## 7.4 Statistical Analyses for Safety

---

Safety analysis will be carried out using the Safety Analysis Set. Incidence of AEs, changes in vital signs, physical examination results, ECGs, and clinical laboratory values will be analyzed. Treatment-emergent AEs will be tabulated by system organ class (SOC) and by Medical Dictionary for Regulatory Activities (MedDRA) preferred term (PT) for the treatment group. Mean change from Baseline for laboratory and vital signs data will be summarized. In addition, shift tables and listings will be provided for abnormal values, whereby the normal range of the analyzing laboratory will be used. Vital signs will be analyzed similarly.

Missing safety data will not be imputed. Details for each safety endpoint analysis will be provided in the SAP.

## 8 ETHICS

### 8.1 Independent Ethics Committee/Institutional Review Board (IEC/IRB)

---

The protocol, informed consent form(s), recruitment materials, and all subject materials will be submitted to the IEC/IRB for review and approval. Approval of both the protocol and the informed consent form(s) must be obtained before any subject is enrolled. Any amendment to the protocol will require review and approval by the IEC/IRB before the changes are implemented to the study. In addition, all changes to the consent form(s) will be IEC/IRB approved.

### 8.2 Ethical Conduct of the Study

---

The study will be conducted in accordance with the protocol, Operations Manual ([Appendix F](#)), International Council for Harmonisation (ICH) guidelines, applicable regulations, and guidelines governing clinical study conduct and the ethical principles that have their origin in the Declaration of Helsinki. Responsibilities of the investigator are specified in [Appendix B](#). Investigators should notify AbbVie if any urgent safety measures are taken to protect the subjects against any immediate hazard.

### 8.3 Subject Confidentiality

---

To protect subjects' confidentiality, all subjects and their associated samples will be assigned numerical study identifiers or "codes." No identifiable information will be provided to AbbVie.

## 9 SOURCE DOCUMENTS AND CASE REPORT FORM COMPLETION

The investigator is responsible for ensuring the accuracy, completeness, legibility, and timeliness of the data reported. All source documents should be attributable, legible, contemporaneous, original, accurate, and complete to ensure accurate interpretation of data. Clinical site monitoring is conducted to ensure that the rights and well-being of human subjects are protected, that the reported trial data are accurate, complete, and verifiable, and that the conduct of the trial is in compliance with the currently approved protocol, ICH Good Clinical Practice (GCP), and applicable local regulatory requirement(s). In cases of state of emergency or pandemic situations, remote monitoring of data may be employed if allowed by the local regulatory authority, IRB/IEC, and the study site.

## 10 DATA QUALITY ASSURANCE

AbbVie will ensure that the clinical trial is conducted with a quality management system that will define quality tolerance limits in order to ensure human subject protection and reliability of study results. Data will be generated, documented, and reported in compliance with the protocol, ICH GCP, and applicable regulatory requirements.

## 11 COMPLETION OF THE STUDY

The end-of-study is defined as 84 days after the last subject last dose of ravagalimab.

## APPENDIX A. STUDY SPECIFIC ABBREVIATIONS AND TERMS

Abbreviation	Definition
5-ASA	5-aminosalicylic acid
6-MP	Mercaptopurine
ADA	Anti-drug antibody
AE	Adverse event
ALT	Alanine transaminase
APC	Antigen presenting cell
AST	Aspartate transaminase
AZA	Azathioprine
bw	body weight
CD	Crohn's disease
CHO	Chinese hamster ovary
CL/F	Apparent clearance
COVID-19	Coronavirus Disease-2019
CTCAE	Common Terminology Criteria for Adverse Events
CXR	Chest X-ray
DILI	Drug-induced liver injury
DMC	Data Monitoring Committee
ECG	Electrocardiogram
eCRF	Electronic case report form
EDP	Extemporaneous Dose Preparation
EIM	Extraintestinal manifestation
eow	Every other week
FAS	Full analysis set
FCP	Fecal calprotectin
FDA	Food and Drug Administration
FSH	Follicle-stimulating hormone
GCP	Good clinical practice
GFR	Glomerular filtration rate
GLP	Good Laboratory Practice
HIV	Human immunodeficiency virus
hs-CRP	High sensitivity C-reactive protein

IBDQ	Inflammatory Bowel Disease Questionnaire
IBD-U	Inflammatory Bowel Disease-unclassified
ICH	The International Council for Harmonisation of Technical Requirements for Pharmaceuticals for Human Use
IEC	Independent ethics committee
IM	Intramuscular
IMP	Investigational Medicinal Product
IRB	Institutional review board
IRT	Interactive response technology
IUD	Intrauterine device
IUS	Intrauterine hormone-releasing system
IV	Intravenous(ly)
JAK	Janus kinase
L	Ligand
mAb	Monoclonal antibody
MDRD	Modification of Diet in Renal Disease
MedDRA	Medical Dictionary for Regulatory Activities
MTX	Methotrexate
nAb	Neutralizing antibody
NOAEL	No-observed-adverse-effect-level
NRI	Non-Responder Imputation
OL	Open-label
PD	Premature discontinuation
PK	Pharmacokinetic(s)
PO	orally ( per os )
POC	Proof of concept
PPD	Purified protein derivative
PT	Preferred term
QTcF	Fridericia-corrected QT interval
RA	Rheumatoid arthritis
RBS	Rectal bleeding subscore
RO	Receptor occupancy
S1P	Sphingosine-1-phosphate
SAE	Serious adverse event

SAP	Statistical analysis plan
SARS-CoV-2	severe acute respiratory syndrome coronavirus 2
SC	Subcutaneous(ly)
SFS	Stool frequency subscore
SLE	Systemic lupus erythematosus
SOC	System organ class
SUSAR	Suspected unexpected serious adverse reactions
TA MD	Therapeutic Area Medical Director
TB	Tuberculosis
Tdap	Tetanus, diphtheria, pertussis vaccine
TNF	Tumor necrosis factor
UC	Ulcerative colitis
UCEIS	Ulcerative Colitis Endoscopic Index of Severity
ULN	Upper limit of normal
Vss/F	Volume of distribution at steady-state
WBC	White blood cell

## APPENDIX D. ACTIVITY SCHEDULE

The following table shows the required activities the subject encounters. The individual activities are described in detail in [Appendix F](#). Allowed modifications due to states of emergency or pandemic situations are detailed within the Operations Manual.

## Study Activities Induction Period

Activity	Screening	Induction Period (W0 to W12)								PD	Unscheduled	84-Day Follow Up Visit a
		Baseline	W2	W4	W6	W8	W10	W12				
	D -35 to D -1	D1	D15 ± 7 days	D29 ± 7 days	D43 ± 7 days	D57 ± 7 days	D71 ± 7 days	D85 ± 7 days				
INTERVIEWS & QUESTIONNAIRES												
Informed consent	✓											
Eligibility criteria	✓	✓										
Medical/surgical history	✓	✓										
Adverse event assessment	✓	✓	✓	✓	✓	✓	✓	✓	✓	✓	✓	✓
Prior/concomitant therapy	✓	✓	✓	✓		✓			✓	✓	✓	
TB Risk Factor Questionnaire	✓											
Subject questionnaires: IBDQ		✓				✓			✓	✓		
Dispense subject diary	✓											
Review subject diary		✓	✓	✓	✓		✓		✓	✓	✓	
LOCAL LABS, EXAMS & ASSESSMENTS												
Height	✓											
Weight	✓	✓				✓			✓	✓		
12-lead ECG b	✓											
Chest X-Ray c	✓											
Vital signs	✓	✓	✓	✓		✓			✓	✓	✓	
Physical examination	✓	✓				✓			✓	✓		
Endoscopy	✓					✓				✓ d		
Partial Adapted Mayo		✓	✓	✓	✓		✓		✓	✓	✓	

Activity	Screening	Induction Period (W0 to W12)							PD	Unscheduled	84-Day Follow Up Visit a
		Baseline	W2	W4	W6	W8	W10	W12			
		D -35 to D -1	D1	D15 ± 7 days	D29 ± 7 days	D43 ± 7 days	D57 ± 7 days	D71 ± 7 days			
Adapted Mayo/Full Mayo			✓				✓			✓	
SARS-CoV-2 molecular test, if applicable	✓										
CENTRAL LABS											
Hepatitis B, Hepatitis C Screening and HIV Test (Note: HBV testing is done every 12 weeks where required)	✓										
C. difficile toxin	✓										
Pregnancy test e	✓ f	✓ g	✓	✓	✓	✓	✓	✓	✓	✓	
FSH f	✓										
QuantiFERON-TB Gold test (and/or local PPD skin test)	✓										
Urinalysis h	✓	✓		✓		✓		✓	✓	✓	
Chemistry and hematology h	✓	✓ g	✓	✓		✓		✓	✓	✓	✓
hs-CRP h		✓	✓	✓		✓		✓	✓	✓	
Serum ravigalimab		✓	✓	✓		✓		✓	✓	✓	
Serum ADA and neutralizing anti-drug antibodies (nAb)		✓		✓				✓	✓	✓	
Biomarker: CD40 RO and/or T cells, NK cells and B cell subsets (including plasmablasts) i		✓		✓		✓		✓	✓	✓	
FCP h,j		✓				✓		✓	✓	✓	
Intestinal Biopsies k	✓					✓			✓ d		
Biomarker Sample: Whole Blood Epigenetic (DNA)		✓				✓		✓	✓	✓	

Activity	Screening	Induction Period (W0 to W12)							PD	Unscheduled	84-Day Follow Up Visit a
		Baseline	W2	W4	W6	W8	W10	W12			
	D -35 to D -1	D1	D15 ± 7 days	D29 ± 7 days	D43 ± 7 days	D57 ± 7 days	D71 ± 7 days	D85 ± 7 days			
Biomarker Sample: Whole Blood Transcriptomic (RNA)		✓				✓			✓	✓	
Biomarker: Whole Blood Immunoassays (Plasma)		✓				✓			✓	✓	
Biomarker: Whole blood Immunoassays (Serum)		✓				✓			✓	✓	

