### Study Activities Maintenance Period (Weeks 12 - 104)

Activity	Maintenance Period (W12 to W104)											PD	Unscheduled	84-Day Follow Up Visit b
	W12 a	W16	W20	W28	W36	W44	W52	W64	W76	W88	W104			
	D85 ± 7 days	D113 ± 7 days	D141 ± 7 days	D197 ± 7 days	D253 ± 7 days	D309 ± 7 days	D365 ± 7 days	D449 ± 7 days	D533 ± 7 days	D617 ± 7 days	D729 ± 7 days			
❑ INTERVIEWS & QUESTIONNAIRES														
Adverse event assessment		✓	✓	✓	✓	✓	✓	✓	✓	✓	✓	✓	✓	✓
Concomitant therapy		✓	✓	✓	✓	✓	✓	✓	✓	✓	✓	✓	✓	
Subject questionnaires: IBDQ							✓				✓	✓		
TB risk factor questionnaire							✓				✓	✓		
Review subject diary		✓	✓	✓	✓	✓	✓	✓	✓	✓	✓	✓	✓	
✚ LOCAL LABS, EXAMS, & ASSESSMENTS														
Weight							✓				✓	✓		
Vital signs		✓	✓	✓	✓	✓	✓	✓	✓	✓	✓	✓	✓	
Physical examination				✓			✓		✓		✓	✓		
Endoscopy							✓				✓	✓		
Partial Adapted Mayo		✓	✓	✓	✓	✓	✓	✓	✓	✓	✓	✓	✓	
Adapted Mayo/Full Mayo							✓				✓	✓		

Activity	Maintenance Period (W12 to W104)											PD	Unscheduled	84-Day Follow Up Visit b
	W12 a	W16	W20	W28	W36	W44	W52	W64	W76	W88	W104			
	D85 ± 7 days	D113 ± 7 days	D141 ± 7 days	D197 ± 7 days	D253 ± 7 days	D309 ± 7 days	D365 ± 7 days	D449 ± 7 days	D533 ± 7 days	D617 ± 7 days	D729 ± 7 days			
CENTRAL LABS														
Pregnancy test c		✓	✓	✓	✓	✓	✓	✓	✓	✓	✓			
Urinalysis d		✓	✓	✓	✓	✓	✓	✓	✓	✓	✓			
Chemistry and hematology d		✓	✓	✓	✓	✓	✓	✓	✓	✓	✓			✓
hs-CRP d				✓			✓		✓		✓			
QuantiFERON-TB-Gold test (and/or local PPD skin test) e							✓				✓			
Serum ravagalimab								✓				✓	✓	
Serum ADA and nAb								✓				✓	✓	
Biomarker: CD40 RO and T cells, NK cells and B cell subsets (including plasmablasts) f								✓					✓	
FCp d,g								✓					✓	
Intestinal Biopsies h,i								✓				✓	✓	
Biomarker Sample: Whole Blood Epigenetic (DNA) i			✓				✓						✓	
Biomarker Sample: Whole Blood Transcriptomic (RNA) i				✓			✓						✓	
Biomarker: Whole Blood Immunoassays (Plasma) i				✓			✓						✓	
Biomarker: Whole blood Immunoassays (Serum) i				✓			✓						✓	
Rx TREATMENT														
Administer study drug j	✓	✓	✓	✓	✓	✓	✓	✓	✓	✓	✓			

a. Study drug dispensation, the only study activity indicated for the maintenance period Week 12 visit, is only for subjects who continue onto the maintenance period.

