### INTERVIEW

- AE assessment
- Chemistry and hematologyk

NOTE: 84-Day Follow-up may be performed as a call if a visit is not possible.

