## 3.2 Medical History and Prior/Concomitant Medications

---

A complete list of prior/concomitant medications and medical history including demographics, history of tobacco, alcohol, and drug use will be taken at screening. The subject's prior/concomitant medications and medical history will be updated at the Study Day 1 visit. This updated medical history will serve as the baseline for clinical assessment. Concomitant medications will be reviewed at each study visit listed in Section 2.1.

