7.3 Prior and Concomitant Medications

Prior and concomitant medications will be summarized by generic name. A prior medication is defined as any medication taken prior to the date of the first dose of study drug. A concomitant medication is defined as any medication that started prior to the date

of the first dose of study drug and continued to be taken after the first dose of study drug or any medication that started on or after the date of the first dose of study drug, but not after the date of the last dose of study drug plus 84 days. The number and percentage of subjects taking medications will be summarized by generic drug name based on the World Health Organization (WHO) Drug Dictionary for both prior and concomitant medications.

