9.2.1 Treatment-Emergent Adverse Events

Treatment-emergent AEs are defined as any AE with the onset that is on or after the first dose of study drug to the last dose date prior to cut-off date + 84 days or the cut-off date for database lock, whichever occurs first. Events where the onset date is the same as the study drug start date are assumed to be treatment emergent. All treatment-emergent AEs will be summarized overall, as well as by primary MedDRA SOC and Preferred

Term. The SOCs will be presented in alphabetical order, and the PTs will be presented in alphabetical order within each SOC.

The number and percentage of subjects experiencing treatment-emergent AEs will be summarized.

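### The 84-day follow-up omits concomitant medication, although the SAP counts medications, adverse events and exposure to 84 days after the last dose

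*Protocol*

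**What the plan says.** **Schedules.** Protocol Appendix D has one concomitant-therapy row per treatment period. The induction row, "Prior/concomitant therapy", is ticked at Screening, Baseline, Weeks 2, 4, 8 and 12, PD and Unscheduled. The maintenance row, "Concomitant therapy", is ticked from Week 16 to Week 104, at PD and at Unscheduled. Both are blank under the 84-day follow-up, where AE assessment and chemistry/hematology are ticked.

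**Visit list.** Operations Manual 2.1 gives the 84-day follow-up two activities: AE assessment and chemistry/hematology. Its note adds: "84-Day Follow-up may be performed as a call if a visit is not possible".

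**General rule.** Operations Manual 3.2 states: "Concomitant medications will be reviewed at each study visit listed in Section 2.1". The 84-day follow-up is one of the visits in Section 2.1.

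**Analysis windows.** SAP 7.3 classes a drug started on treatment as concomitant if it began on or after the first dose "but not after the date of the last dose of study drug plus 84 days". SAP 9.2.1 counts treatment-emergent AEs "to the last dose date prior to cut-off date + 84 days", or to the database cut-off if that comes first. The exposure denominator in SAP 9.1 also adds 84 days to the dosing interval.

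**Treatment after stopping.** Protocol 4.1 sends Week 12 non-responders, and those who complete maintenance, to a follow-up contact 84 days after the last dose. Operations Manual 3.13 leaves treatment after study drug stops to the investigator's judgment and says study procedures should not delay new treatment.

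**The concern.** The SAP analyses an 84-day post-dose window, but the contact that closes the window is not scheduled to ask which drugs were taken during it. The subjects most affected are Week 12 non-responders: they have refractory disease, have just been taken off study drug, and may well start another UC therapy in that period.

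Two outputs suffer. The concomitant-medication table would miss many drugs started late in its own window. The treatment-emergent AE, AESI and exposure-adjusted tables could not be reliably divided into events before and after a new UC therapy. SAP section 9 has no rule that flags or separates such events; the corticosteroid rule in SAP 8.1 concerns efficacy endpoints during induction. In a single-arm study there is little concurrent comparison to help interpret infections, hepatic events or cytopenias that follow a switch.

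**Working it through.** The plan gives no figure for this gap, so there is none to reproduce. The check is a comparison of passages followed by day arithmetic.

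**Is the blank cell real?** The extracted tables are imperfect, so the cell was checked against the text. The Operations Manual list for the 84-day follow-up has no concomitant-medication item, while the lists for PD and Unscheduled visits in both periods name it. The two sources agree that it is absent.

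**Inputs**
- Study day = 7 × week + 1, which matches the Appendix D headings (Week 12 = Day 85, Week 104 = Day 729).
- Last induction dose: Week 10, Day 71. Last scheduled medication review for a non-responder: Week 12, Day 85.
- Last maintenance dose: Week 102 (Operations Manual 2.1), Day 7 × 102 + 1 = 715. Last scheduled review for a completer: Week 104, Day 729.
- Window end = last dose + 84 days (SAP 7.3 and 9.2.1).
- Exposure = last dose − first dose + 84 days (SAP 9.1), with first dose on Day 1.
- Gap = window end − last scheduled review.

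**Results**

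| | Week 12 non-responder | Completer |
|---|---|---|
| Window end | 71 + 84 = Day 155 | 715 + 84 = Day 799 |
| Gap | 155 − 85 = 70 days | 799 − 729 = 70 days |
| Share of the 84 days | 70/84 = 83% | 70/84 = 83% |
| Exposure | 71 − 1 + 84 = 154 days | 715 − 1 + 84 = 798 days |
| Gap as share of exposure | 70/154 = 45% | 70/798 = 9% |

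**Visit window.** With the last dose on its nominal day and the last review moved by ±7 days, the gap runs from 70 − 7 = 63 days (63/84 = 75%) to 70 + 7 = 77 days (77/84 = 92%).

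**After the fix.** A review at the 84-day contact that covers the time since the previous review reduces the gap to 0 for both groups.

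**The case against.** **Operations Manual 3.2 already requires the review.** Read literally it does, so the documents contradict each other; they do not deliberately exclude the data. That part stands. It does not close the gap, because the visit's own list and both schedules say otherwise. The Week 6 and Week 10 visits are also in Section 2.1 without a medication review, so the general sentence does not govern every listed visit. A site working from the visit list would not ask.

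**Other routes capture medication.** PD and Unscheduled visits collect it. Protocol 5.6 keeps premature discontinuers on regular visits, most of which include the review. Protocol 6.1 provides supplemental forms for some AESIs, and Protocol 6.2 has an alternative etiology recorded for ALT/AST elevations meeting Table 2. A reader might infer that a switch would leave no trace in the database; the documents do not support that. The accurate statement is that no collection is scheduled. These routes do not replace a routine question for Week 12 non-responders, whom Protocol 4.1 sends directly to the 84-day contact.

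**Treatment-emergent is a matter of timing, not cause.** A reader might infer that post-switch events are attributed to ravagalimab. They enter the treatment-emergent, AESI and exposure-adjusted counts, but Protocol 6.1 has the investigator rate relatedness separately, weighing alternative causes, and SAP 9.2.3 tabulates events by that rating.

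**Direction.** A reader might also infer that the gap undermines a conclusion that the drug is safe and well tolerated. Counting post-switch events adds to the ravagalimab totals, which would make the drug look less safe. The loss is in interpretation; no harm is concealed.

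**SAP 7.3 only classifies recorded drugs.** It sets a date limit and does not promise complete ascertainment. That is fair, but a table defined to Day +84 is still likely to be incomplete when scheduled collection stops about 14 days after the last dose.

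**Conclusion.** The concern holds as an inconsistency with a practical consequence. Both schedules and the 84-day visit list omit concomitant medication, against Operations Manual 3.2 read literally and against SAP windows that run to last dose plus 84 days. About 70 of those 84 days (63 to 77) have no scheduled collection for Week 12 non-responders and Week 104 completers. The weight differs between the groups: about 45% of exposure time for a non-responder and about 9% for a completer.

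The figures assume nominal dosing days, no PD or Unscheduled visit in the gap, and a window not cut short by a database cut-off. The documents give neither the expected number of non-responders nor the proportion who would start another therapy, so neither the number of subjects nor the number of AEs affected can be estimated. The Week 8 primary endpoint is untouched. The finding concerns the completeness of one planned table and the interpretability of the post-dose AE counts.

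**What to change.** 1. **Protocol Appendix D:** tick concomitant therapy under the 84-day follow-up in both the induction and maintenance tables.
2. **Operations Manual 2.1:** add a concomitant-medication assessment to the 84-day list, covering the whole time since the last review, whether the contact is a visit or a call. Word Operations Manual 3.2 so that it agrees with the visit lists.
3. **SAP 9.2.1:** keep the treatment-emergent definition. As a supplementary display, flag treatment-emergent AEs with onset after the start of a new UC therapy and show counts with and without them.

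The cost is one more item at a contact that already takes place, slightly more site data entry, and one derived flag in the AE tables. The supplementary display is a recommendation; nothing in the documents requires it. The reconciliation in steps 1 and 2 is needed in any case.

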## Rx TREATMENT

Enrollment		✓									
Administer study drug 		✓	✓	✓	✓	✓	✓				
Review subject diary		✓	✓	✓		✓			✓	✓	✓

- The 84-day follow up visit (or call if a visit is not possible) will be calculated from the last study drug administration date.
- Repeat ECG will be performed as needed at the discretion of the investigator throughout the study.
- CXR will be performed only on those subjects with positive Quantiferon and/or PPD test.
- If the subject discontinues between Week 4 and Week 8, endoscopy will be performed at the PD visit. If the subject discontinues after Week 8, during the Induction Period, endoscopy will not be performed at the PD visit.
- Serum pregnancy test will be performed on all females of childbearing potential at Screening. Urine pregnancy test will be performed locally as indicated in the table for all females of childbearing potential. The urine pregnancy test must be negative to receive study drug. If any urine pregnancy test is positive, a serum pregnancy test will be performed by the central laboratory.
- Only for women ≤ age 55, no menses for > 12 months, and no history of permanent surgical sterilization to confirm postmenopausal status.
- Lab assessments will only need to be repeated at Baseline if the time between Screening and Baseline is greater than 14 days, or if the subject's health status has changed to warrant a repeat test.
- Urinalysis, chemistry and hematology, hs-CRP, and FCP may be collected at other scheduled and unscheduled visits than indicated in the table if they are warranted by the Investigator.
- T cells, NK cells and B cells subsets (including plasmablasts) will be analyzed at all indicated study visits. CD40 RO will only be analyzed at Baseline, Week 8 and Week 52 and PD if prior to Week 52.

- j. Stool sample will be collected at each time point indicated in the table. For the visit when endoscopy will be conducted, stool sample should be collected prior to bowel prep and should be returned to the site within 3 days of collection. If a sample cannot be obtained during the site visit, the site will give instructions and a stool sample supply kit.
- k. Mandatory intestinal biopsies will be collected for histopathology, gene expression, and tissue RO (where applicable). Additional biopsies may also be collected at the Investigator's discretion to confirm disease diagnosis and/or to rule out dysplasia, colon cancer and infection.
- l. Consecutive doses should not be administered less than a week (7 days) apart.

### Study Activities Maintenance Period (Weeks 12 - 104)

Activity	Maintenance Period (W12 to W104)											PD	Unscheduled	84-Day Follow Up Visit b
	W12 a	W16	W20	W28	W36	W44	W52	W64	W76	W88	W104			
	D85 ± 7 days	D113 ± 7 days	D141 ± 7 days	D197 ± 7 days	D253 ± 7 days	D309 ± 7 days	D365 ± 7 days	D449 ± 7 days	D533 ± 7 days	D617 ± 7 days	D729 ± 7 days			
❑ INTERVIEWS & QUESTIONNAIRES														
Adverse event assessment		✓	✓	✓	✓	✓	✓	✓	✓	✓	✓	✓	✓	✓
Concomitant therapy		✓	✓	✓	✓	✓	✓	✓	✓	✓	✓	✓	✓	
Subject questionnaires: IBDQ							✓				✓	✓		
TB risk factor questionnaire							✓				✓	✓		
Review subject diary		✓	✓	✓	✓	✓	✓	✓	✓	✓	✓	✓	✓	
✚ LOCAL LABS, EXAMS, & ASSESSMENTS														
Weight							✓				✓	✓		
Vital signs		✓	✓	✓	✓	✓	✓	✓	✓	✓	✓	✓	✓	
Physical examination				✓			✓		✓		✓	✓		
Endoscopy							✓				✓	✓		
Partial Adapted Mayo		✓	✓	✓	✓	✓	✓	✓	✓	✓	✓	✓	✓	
Adapted Mayo/Full Mayo							✓				✓	✓		

Activity	Maintenance Period (W12 to W104)											PD	Unscheduled	84-Day Follow Up Visit b
	W12 a	W16	W20	W28	W36	W44	W52	W64	W76	W88	W104			
	D85 ± 7 days	D113 ± 7 days	D141 ± 7 days	D197 ± 7 days	D253 ± 7 days	D309 ± 7 days	D365 ± 7 days	D449 ± 7 days	D533 ± 7 days	D617 ± 7 days	D729 ± 7 days			
CENTRAL LABS														
Pregnancy test c		✓	✓	✓	✓	✓	✓	✓	✓	✓	✓			
Urinalysis d		✓	✓	✓	✓	✓	✓	✓	✓	✓	✓			
Chemistry and hematology d		✓	✓	✓	✓	✓	✓	✓	✓	✓	✓			✓
hs-CRP d				✓			✓		✓		✓			
QuantiFERON-TB-Gold test (and/or local PPD skin test) e							✓				✓			
Serum ravagalimab								✓				✓	✓	
Serum ADA and nAb								✓				✓	✓	
Biomarker: CD40 RO and T cells, NK cells and B cell subsets (including plasmablasts) f								✓					✓	
FCp d,g								✓					✓	
Intestinal Biopsies h,i								✓				✓	✓	
Biomarker Sample: Whole Blood Epigenetic (DNA) i			✓				✓						✓	
Biomarker Sample: Whole Blood Transcriptomic (RNA) i				✓			✓						✓	
Biomarker: Whole Blood Immunoassays (Plasma) i				✓			✓						✓	
Biomarker: Whole blood Immunoassays (Serum) i				✓			✓						✓	
Rx TREATMENT														
Administer study drug j	✓	✓	✓	✓	✓	✓	✓	✓	✓	✓	✓			

a. Study drug dispensation, the only study activity indicated for the maintenance period Week 12 visit, is only for subjects who continue onto the maintenance period.

- b. The 84-day follow up visit (or call if a visit is not possible) will be calculated from the last study drug administration date.
- c. Urine pregnancy test will be performed locally as indicated in the table for all females of childbearing potential. The urine pregnancy test must be negative to receive study drug. If any urine pregnancy test is positive, a serum pregnancy test will be performed by the central laboratory.
- d. Urinalysis, chemistry and hematology, hs-CRP, and FCP may be collected at other scheduled and unscheduled visits than indicated in the table if they are warranted by the Investigator.
- e. For subjects with a negative TB test, an annual TB test will be required at Weeks 52 and 104. If the annual TB screen is positive, a CXR will be required for evaluation of active TB. Annual TB screening will not be required for subjects who have been treated for latent, or prior active, TB.
- f. T cells, NK cells and B cells subsets (including plasmablasts) will be analyzed at all indicated study visits. CD40 RO will only be analyzed at Baseline, Week 8 and Week 52/PD.
- g. Stool sample will be collected at each time point indicated in the table. For the visit when endoscopy will be conducted, stool sample should be collected prior to bowel prep and should be returned to the site within 3 days of collection. If a sample cannot be obtained during the site visit, the site will give instructions and a stool sample supply kit.
- h. Mandatory intestinal biopsies will be collected for histopathology, gene expression, and tissue RO (where applicable). Additional biopsies may also be collected at the Investigator's discretion to confirm disease diagnosis and/or to rule out dysplasia, colon cancer and infection.
- i. Only to be collected at PD visit if subject discontinues prior to Week 52.
- j. Consecutive doses should not be administered less than a week (7 days) apart.

